5.3.3.1 Subgroup Analyses for Primary Endpoint

The consistency of \geq 2-step improvement from baseline on the ETDRS-DRSS results when comparing PDS and comparator arms will be investigated by estimating the treatment effect in subgroups based on age, (< 65 years, \geq 65 years) sex (male, female), race (White, non-White), ethnicity (Hispanic, non-Hispanic), baseline ETDRS-DRSS (DRSS 47 vs DRSS 53), and glycosylated hemoglobin (HbA1c) (< 8.0%, \geq 8.0%). Due to small numbers in some subgroups, the analyses will use Fisher's exact test with unadjusted proportions. The estimand and data handling rules follow those for the main analysis for the primary endpoint (see Section 5.3.2). Point estimates of treatment group differences in \geq 2-step improvement with 95.04% CIs will be provided in forest plots.

5.4 SECONDARY EFFICACY ENDPOINTS ANALYSES

5.4.1 Key/Confirmatory Secondary Endpoints

5.4.1.1 Rate of Patients Developing a Vision Threatening Complication (Defined As PDR or ASNV) or CI-DME through Week 52

The rate of patients developing vision-threatening complications (defined as PDR or ASNV) or CI-DME (defined as CST \geq 325 µm) through Week 52 will be estimated using the Kaplan-Meier method based on time from randomization to the time the first such event occurs. The estimand for the endpoint will be as follows:

- Population: Adult patients with moderately severe or severe NPDR (ETDRS-DRSS level 47 or 53) and no presence of CI-DME who are naive to any treatment for DR in the study eye
- Variable: same as the endpoint
- Intercurrent events which occur prior to Week 52:
 - Receiving any supplemental treatment: A composite variable strategy will be applied where the intercurrent event is considered to be an event in the analysis.
 - b) Receiving any prohibited therapy or PRP, including prohibited therapy or PRP administered post study treatment discontinuation: A composite variable strategy will be applied where the intercurrent event is considered to be an event in the analysis.
 - c) Discontinuing study treatment (PDS arm) or discontinuing study (comparator arm) due to an AE: A treatment policy strategy will be applied where all observed values will be used regardless of the occurrence of the intercurrent event.
 - d) Discontinuing study treatment (PDS arm) or discontinuing study (comparator arm) due to lack of efficacy per Investigator's judgment: A treatment policy strategy will be applied where all observed values will be used regardless of the occurrence of the intercurrent event.
- Population-level summary: Event rates in PDS and comparator arms through Week
 52, grouped as assigned at randomization, with p-value and hazard ratio (HR) for the difference.

The rate of patients developing vision-threatening complications or CI-DME through Week 52 will be estimated using the Kaplan-Meier method. A stratified log-rank test will be used for hypothesis testing comparing the PDS arm with the comparator arm with respect to time to the respective event. A Cox proportional hazards regression model will be used as a supportive analysis to estimate the HR and its 95.04% CI. The model will include treatment arm and will be stratified based on the stratified randomization factors as per IxRS. Patients who do not experience vision-threatening complications or CI-DME will be censored at the end of their time at risk (last visit at or before Week 52). The HR and 95.04% CI for the treatment effect (PDS vs. comparator) will be calculated based on the model.

5.4.1.2 Rate of Patients Developing PDR or ASNV through Week 52

The rate of patients developing PDR or ASNV through Week 52 will be analyzed using the same analysis method, estimand and data handling rules as Section 5.4.1.1.

5.4.1.3 Rate of Patients Developing CI-DME through Week 52

The rate of patients developing CI-DME (defined as CST \geq 325 μ m) through Week 52 will be analyzed using the same analysis method, estimand and data handling rules as Section 5.4.1.1.

5.4.1.4 Rate of Patients Developing ≥ 2-step Worsening from Baseline on the ETDRS-DRSS through Week 52

The rate of patients developing \geq 2-step worsening from baseline on the ETDRS-DRSS through Week 52 will be analyzed using the same analysis method, estimand and data handling rules as Section 5.4.1.1.

5.4.1.5 Proportion of Patients with ≥ 3 Step Improvement from Baseline on the ETDRS DRSS at Week 52

The proportion of patients with a \geq 3-step improvement from baseline on the ETDRS-DRSS at Week 52 will be analyzed using Fisher's exact test with unadjusted proportions. The estimand and data handling rules follow those for the main analysis for the primary endpoint (see Section 5.3).

5.4.1.6 Rate of Patients Developing ≥ 3-step Worsening from Baseline on the ETDRS-DRSS through Week 52

The rate of patients developing \geq 3-step worsening from baseline on the ETDRS-DRSS through Week 52 will be analyzed using the same analysis method, estimand and data handling rules as Section 5.4.1.1.

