for which, P_{PDS} and P_{C} refer to proportion of patients who achieve a \geq 2-step improvement from baseline on the ETDRS-DRSS for PDS arm and comparator arm, respectively.

For the key secondary endpoints numbers 2-5 and 7 listed in Section 2.1 that are based on rate, the null and alternative hypotheses are as follows:

The null hypothesis (H_o) is: $S_{PDS}(t) = S_C(t)$; for t in (0,52 Weeks).

The alternative hypothesis (H_a) is: $S_{PDS}(t) \neq S_C(t)$.

for which, $S_{PDS}(t)$ and $S_C(t)$ refer to the survival functions for PDS arm and comparator arm, respectively.

For the key secondary endpoint number 6 listed in Section 2.1 based on proportion, the null and alternative hypotheses will follow the same form as those of the primary endpoint.

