5.1 GENERAL CONSIDERATION

Efficacy analyses will be based on the intent-to-treat (ITT) Population unless otherwise specified.

Descriptive summaries will include the mean, standard deviation (SD), median, and range for continuous variables, and counts and percentages for categorical variables. Missing data for descriptive summaries will not be imputed unless otherwise noted.

For all efficacy endpoints, comparative efficacy analyses will be performed during the comparator-controlled treatment period (randomization through Week 60). At the primary

analysis, only the efficacy assessments collected through Week 52 will be included in the comparative efficacy analyses and descriptive summaries. At the final (end of study) analysis only the efficacy assessments collected through Week 60 will be included in the comparative efficacy analyses and data collected through end of study will be included in summaries. For the safety summaries, only data reported through Week 52 will be included at the time of the primary analysis. At the time of the final analysis, safety summaries will include all safety data collected through end of study (see Section 5.6).

Unless otherwise noted, analyses of efficacy outcome measures will be stratified by the randomization stratification factors (ETDRS-DRSS level [47 vs. 53] and intraretinal or subretinal fluid status on SD-OCT [present vs. absent] as assessed at baseline by a central reading center) as recorded in IxRS.

A nominal type I error penalty of 0.0001 (two-sided) will be taken for each time the iDMC conducts an unmasked interim safety review prior to the primary analysis. At the time of the primary analysis, four interim data reviews have been conducted by the iDMC; therefore, efficacy analyses will be performed at a significance level of 0.0496. All CIs will be two-sided and at the 95.04% level.

The occurrence of each type of intercurrent event as defined in Section 5.3.1 will be summarized by treatment arm. Additionally, the occurrence of each type of intercurrent event due to coronavirus disease of 2019 (COVID-19) as defined in the supplementary analysis in Section 5.3.3 will be summarized by treatment arm.

Data collected in selected scheduled and unscheduled visits will be mapped to visits that appear in the schedule of assessments (see Appendix 1 of the Protocol) per the Protocol using the actual study day of assessment.

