5.3 PRIMARY EFFICACY ENDPOINT ANALYSIS

5.3.1 Definition of Primary Endpoint

The primary efficacy endpoint is the proportion of patients with a \geq 2-step improvement from baseline on the ETDRS-DRSS at Week 52, where DRSS is assessed by a masked central reading center. The primary estimand is defined as follows:

- Population: Adult patients with moderately severe or severe NPDR (ETDRS-DRSS level 47 or 53) and no presence of CI-DME who are naive to any treatment for DR in the study eye
- Variable: $A \ge 2$ -step improvement from baseline on the ETDRS-DRSS at Week 52
- Intercurrent events which occur prior to Week 52:
 - a) Receiving any supplemental treatment: A composite variable strategy will be applied. Patients with this intercurrent event will be regarded as non-responders (i.e., they are regarded as not achieving 2-step improvement on the EDTRS-DRSS).
 - b) Receiving any prohibited therapy (as defined in Section 4.4.2 of the Protocol, including prohibited therapy administered post study treatment discontinuation), or PRP in the study eye: A composite variable strategy will be applied where patients with this intercurrent event will be regarded as non-responders.

- c) Discontinuing study treatment (PDS arm) or discontinuing study (comparator arm) due to an AE: A treatment policy strategy will be applied where all observed values will be used regardless of the occurrence of the intercurrent event.
- d) Discontinuing study treatment (PDS arm) or discontinuing study (comparator arm) due to lack of efficacy per Investigator's judgment: A treatment policy strategy will be applied where all observed values will be used regardless of the occurrence of the intercurrent event.
- Population-level summary: Difference in adjusted proportion between PDS and comparator arms as assigned at randomization.

5.3.2 Main Analytical Approach for Primary Endpoint

The primary analysis will be performed using the Cochran–Mantel–Haenszel (CMH) test stratified by baseline ETDRS-DRSS level (47 vs. 53) and intraretinal or subretinal fluid status on SD-OCT (present vs. absent) as assessed at baseline by a central reading center and as recorded in IxRS.

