Patients receiving supplemental treatments, prohibited therapy, or PRP (intercurrent events a-b) may experience an improvement in the ETDRS-DRSS level as a result which would potentially bias the results in favor of an ineffective treatment. Their ETDRS-DRSS level at Week 52 will be imputed using the assumption that they did not have a \geq 2-step improvement from baseline.

ETDRS-DRSS level for patients who discontinue study treatment due to lack of efficacy or AE are unlikely to change in the absence of supplemental treatments, prohibited therapy or PRP and inclusion of data following treatment discontinuation is unlikely to bias results. Therefore, their assessments after the intercurrent events c-d (but before receiving supplemental treatment or prohibited therapy or PRP) will be included in the analyses. For these patients who discontinue study treatment due to lack of efficacy or AE who are also missing ETDRS-DRSS level at Week 52 the last observed ETDRS-DRSS level prior to Week 52 will be imputed.

If there are no post-baseline ETDRS-DRSS levels observed, the baseline level will be imputed (patient regarded as non-responder).

If a patient has more than one intercurrent event, the composite strategy in which patients are included as non-responders will take precedence over the treatment policy strategy.

For patients who do not have intercurrent events a-d and are missing ETDRS-DRSS level (including death) at Week 52, the outcome at Week 52 will be imputed using the last observed outcome prior to Week 52. Patients with missing baseline outcomes will be excluded from the analysis.

The proportion of patients in each treatment group and the overall difference in proportions between treatment groups will be estimated using the weighted average of the observed proportions and the differences in observed proportions over the strata defined by randomization stratification factors of baseline ETDRS-DRSS and baseline intraretinal or subretinal fluid status using the CMH weights (Cochran 1954; Mantel and Haenszel 1959) as recorded in IxRS. CIs of the difference in proportions between treatment groups will be calculated using the normal approximation to the weighted proportions (Mehrotra and Railkar 2000).

5.3.3 Supplementary Analyses for Primary Endpoint

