5.4.2 Additional Secondary Efficacy Endpoints

5.4.2.1 Proportion of Patients with A ≥ 2-step Improvement from Baseline on the ETDRS-DRSS over Time

The proportion of patients with \geq 2-step improvement from baseline on the ETDRS-DRSS over time will be analyzed using the analysis method, estimand and data handling rules following those for the main analysis for the primary endpoint (see Section 5.3) comparatively through Week 52 and with adjusted proportions descriptively through end of study.

5.4.2.2 Proportion of Patients with a ≥ 3-step Improvement from Baseline on the ETDRS-DRSS over Time

The proportion of patients with \geq 3-step improvement from baseline on the ETDRS-DRSS over time will be analyzed using analysis method, estimand and data handling rules as Section 5.4.1.5 comparatively through Week 52, and descriptively through end of study.

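### The normal-approximation interval set for the BCVA and fluid proportions under-covers at some rates near 0% or 100%; a score-type interval is a cheap improvement, and two Fisher-based sections need related wording

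*SAP*

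**What the plan says.** **BCVA and fluid proportions.** Sections 5.4.2.9 (losing fewer than 15, 10 or 5 letters), 5.4.2.10 (69 letters or better) and 5.4.2.13 (absence of fluid) are compared between arms through Week 52 and Week 60. All three specify a normal approximation without adjustment. Section 5.1 adds the level: "All CIs will be two-sided and at the 95.04% level". No alternative is given for extreme rates, and no expected rates are stated.

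**Subgroups of the primary endpoint.** Section 5.3.3.1 uses Fisher's exact test with unadjusted proportions, because some subgroups are small. It says that point estimates of the difference in ≥2-step "improvement with 95.04% CIs will be provided in forest plots". It names no interval method.

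**≥3-step improvement.** Section 5.4.1.5 uses Fisher's "exact test with unadjusted proportions. The estimand and data handling rules follow those for the main analysis for the primary endpoint". The inherited estimand in Section 5.3.1 reads: "Population-level summary: Difference in adjusted proportion between PDS and comparator arms as assigned at randomization". Section 5.4.2.2 extends this to the over-time version, which "will be analyzed using analysis method, estimand and data handling rules as Section 5.4.1.5 comparatively through Week 52". The only interval for a difference in proportions described in the primary analysis is in Section 5.3.2: "CIs of the difference in proportions between treatment groups will be calculated using the normal approximation to the weighted proportions". That one belongs to the CMH-weighted estimate.

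**Default and hypothesis.** Section 5.1: "Unless otherwise noted, analyses of efficacy outcome measures will be stratified by the randomization stratification factors". Section 2 says of the ≥3-step endpoint that "the null and alternative hypotheses will follow the same form as those of the primary endpoint", which is a plain difference in proportions equal to zero.

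**The concern.** The normal interval takes its width from the observed proportions. When an arm shows no failures, or no successes, that arm contributes zero variance and the interval is too narrow or collapses to a point. Proportions such as losing fewer than 15 letters, or having no fluid in the central subfield, could lie near 100%. A reader could then be shown a between-arm interval that is far less reliable than its label.

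In small subgroups the same weakness would appear if the normal method of Section 5.3.2 were borrowed for the forest plots. For the ≥3-step endpoint the issue is wording: the section specifies an unadjusted estimate but inherits a summary that says adjusted, and it does not say which interval would accompany the result if one is shown.

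**Working it through.** **Inputs.** Arms of 100 and 60 (Section 3). Alpha 0.05 − 4 × 0.0001 = 0.0496, so the level is 1 − 0.0496 = 95.04%, as Section 5.1 states; z = 1.9634. Rates of 50% vs 15% for the primary endpoint (Section 3, Appendix 1). Dropout of about 5% at closing of recruitment (Section 3), giving 95 and 57. All BCVA and fluid rates and all subgroup sizes below are assumptions.

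**Formulas.** Let a and b be the observed proportions in the PDS and comparator arms, and d = a − b.
- Normal: d ± z·√[a(1−a)/n₁ + b(1−b)/n₂]. The SAP does not print a formula; this is the usual unpooled form.
- Newcombe: take the Wilson limits (l₁,u₁) and (l₂,u₂) for each arm. Lower = d − √[(a−l₁)² + (u₂−b)²]; upper = d + √[(u₁−a)² + (b−l₂)²].
- Coverage: the sum of binomial probabilities over all 2×2 tables whose interval contains the true difference. This is exact enumeration.

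**Coverage at nominal 95.04%, 100 vs 60.**

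| PDS vs comparator (assumed) | Normal |
|---|---|
| 99% vs 97% (same as 1% vs 3%) | 83.5% |
| 98% vs 96% | 90.2% |
| 97% vs 93% | 92.1% |
| 95% vs 90% | 94.0% |
| 97% vs 99% | 94.3% |
| 85% vs 80% | 94.3% |
| 98% vs 98% | 95.2% |
| 96% vs 98% | 95.9% |
| 99% vs 99% | 98.9% |

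Newcombe covers 95.3% to 99.2% across the same nine settings. With 95 and 57 patients the normal interval gives 82.0% at 99% vs 97%, 89.3% at 98% vs 96%, 93.6% at 97% vs 93%, 92.8% at 97% vs 99% and 92.8% at 95% vs 90%.

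**Where the 83.5% comes from.** At 97% the comparator arm is 60/60 with probability 0.97⁶⁰ = 16.1%. Its variance term is then zero. With 99/100 in the PDS arm, d = −1 point and the half-width is 1.9634 × √(0.99 × 0.01/100) = 1.95 points, so the upper limit is +0.95 and misses the true +2. No other PDS count rescues it. This one event supplies 16.1 of the 16.5 points of non-coverage (100 − 83.5).

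**Zero width.** This happens when both arms are 100%. At 99% vs 97% the probability is 0.99¹⁰⁰ × 0.97⁶⁰ = 5.9%; at 99% vs 99% it is 0.99¹⁶⁰ = 20%. In the second case the true difference is 0, so the collapsed interval counts as covering, which is why 98.9% coverage and a 20% collapse rate coexist. For 100/100 vs 60/60 Newcombe gives −3.7 to 6.0 points.

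**Subgroups at 50% vs 15%, sizes assumed.** Normal: 94.4% at 50/30, 93.4% at 30/18, 92.8% at 20/12, 90.3% at 15/9. Newcombe is about 95% at all four sizes.

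**≥3-step endpoint.** Under exact 5:3 allocation in each stratum, n₁ₖ = 5Nₖ/8 and n₂ₖ = 3Nₖ/8. The CMH weight n₁ₖn₂ₖ/Nₖ is then 15Nₖ/64, proportional to Nₖ, and the weighted difference equals the crude one. In simulation with each of four assumed strata one patient off, the two differ by 0.002 on average and 0.014 at most. If an interval is shown, its choice can matter for reading: for 10/100 vs 1/60, Fisher p = 0.054, the normal interval is 1.6 to 15.1 points and Newcombe −0.2 to 15.9.

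**The case against.** The normal approximation is a standard, stated choice for endpoints outside the fixed sequence, so no confirmatory claim rests on it. Six of the nine settings in the table give at least 94.0%; the worst figure needs 99% vs 97%, a corner the SAP neither assumes nor excludes. For fluid, presence vs absence is a randomisation stratum, so near-universal absence was not an obvious expectation. All of this stands. It limits the size of the point but does not remove it, because an interval that does not fail in the corner costs almost nothing.

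On the ≥3-step endpoint the defence is stronger. A reader might infer that the unstratified Fisher test breaches the plan, that the SAP leaves the nature of the estimate open, or that a conflicting interval could decide whether the last endpoint is tested. The document supports none of these. Section 5.1 allows noted exceptions and Section 5.4.1.5 notes one. Sections 2.1 and 5.4.1.5 together make the Fisher p-value the gate. Fisher's test controls type I error, and the adjusted and unadjusted differences target the same quantity under 5:3 allocation within strata. Section 5.4.1.5 also promises no interval. What remains is one inherited word, adjusted, and an unnamed interval should one be reported.

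A reader might also infer that the normal interval always under-covers near 0% or 100%. It does not: it is near nominal or conservative in several settings above.

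**Conclusion.** The point holds as a low-cost improvement. For the BCVA and fluid proportions, the prescribed interval falls to between 83.5% and 92.1% coverage at three of the nine assumed rate combinations and can collapse to zero width; elsewhere it is adequate or conservative. These figures depend on assumed rates, on 100 and 60 evaluable patients, and on the unpooled form of the interval. For the subgroups, the promised interval has no method. Borrowing the normal one would cost little at 50/30 but about 5 points of coverage at 15/9 (95.04 − 90.3 = 4.7), at the SAP's own design rates and assumed sizes. For the ≥3-step endpoint the defect is wording only. The primary analysis, the Fisher test, the testing sequence and type I error control are not in question.

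**What to change.** 1. Sections 5.4.2.9, 5.4.2.10 and 5.4.2.13: keep the analyses unadjusted, but replace the normal interval for the difference with one named, unstratified score-type interval (Newcombe or Miettinen-Nurminen) at 95.04%.
2. Section 5.3.3.1: name the same interval for the forest plots, and do not carry over the normal approximation of Section 5.3.2.
3. Sections 5.4.1.5 and 5.4.2.2: state that the population-level summary is the unadjusted difference in proportions, with the intercurrent-event and missing-data rules still as in Section 5.3. If an interval is reported, use the same score-type method.

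**Cost.** A few sentences and minor programming with standard procedures; no new data. The intervals will be slightly wider and conservative near the boundary (up to about 99% coverage). An interval and the Fisher p-value may still occasionally disagree; the p-value already governs the testing sequence, so no further rule is needed.

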5.4.1.7 Supplementary Analysis for the Time-to-Event Key Secondary Endpoints

A supplementary analysis will be performed where all intercurrent events from the key secondary endpoints with time-to-event outcomes (i.e. rate of patients developing) are treated as events. The supplementary analysis will represent a conservative non-responder imputation strategy, which regards need for supplemental treatment, prohibited therapy, or PRP, or treatment discontinuation due to AE or lack of efficacy as an event regardless of their observed outcome.

The estimand is defined as follows:

- Population: Adult patients with moderately severe or severe NPDR (ETDRS-DRSS level 47 or 53) and no presence of CI-DME who are naive to any treatment for DR in the study eye
- Variable: Same as the endpoint
- Intercurrent events which occur prior to Week 52: A composite variable strategy will be applied to following intercurrent events: receipt of supplemental intravitreal

ranibizumab 0.5 mg injection treatments, prohibited therapies, PRP, or discontinued study/treatment due to lack of efficacy or AE prior to Week 52, where these intercurrent events will be treated as events in the analysis.

Population-level summary: Event rates in PDS and comparator arms through Week
 52, grouped as assigned at randomization, with p-value and hazard ratio (HR) for the difference.

The same analysis methods described in Section 5.4.1.1 will be used in this supplementary analysis.

5.4.1.8 Supplementary Analysis for the Time-to-Event Key Secondary Endpoints of Patients Developing a Vision Threatening Complication (Defined As PDR or ASNV) or CI-DME

An additional supplementary analysis will be performed for the key secondary endpoints of:

- Rate of patients developing a vision threatening complication (defined as PDR or ASNV) or CI-DME through Week 52
- Rate of patients developing a vision threatening complication (defined as PDR or ASNV) = through Week 52
- Rate of patients developing CI-DME through Week 52

The criteria for receiving supplemental treatment is the development of PDR, ASNV or CI-DME. In the main analysis, receipt of supplemental treatment is an intercurrent event and treated as event in the analysis. This supplementary analysis is included to assess the time to a vision threatening complication or time to CI-DME individually.

Intercurrent events of receipt of supplemental intravitreal ranibizumab 0.5 mg injection treatments, prohibited therapies or PRP will be treated using the hypothetical strategy in which all values will be censored after the intercurrent event.

The estimand is defined as follows:

- Population: Adult patients with moderately severe or severe NPDR (ETDRS-DRSS level 47 or 53) and no presence of CI-DME who are naive to any treatment for DR in the study eye
- Variable: Same as the endpoint
- Intercurrent events which occur prior to Week 52:
 - Receiving any supplemental treatment: A hypothetical strategy will be applied where all values will be censored after the intercurrent event.
 - Receiving any prohibited therapy or PRP, including prohibited therapy or PRP administered post study treatment discontinuation: A hypothetical

- strategy will be applied where all values will be censored after the intercurrent event.
- Discontinuing study treatment (PDS arm) or discontinuing study (comparator arm) due to an AE: A treatment policy strategy will be applied where all observed values will be used regardless of the occurrence of the intercurrent event.
- Discontinuing study treatment (PDS arm) or discontinuing study (comparator arm) due to lack of efficacy per Investigator's judgment: A treatment policy strategy will be applied where all observed values will be used regardless of the occurrence of the intercurrent event.
- Population-level summary: Event rates in PDS and comparator arms through Week
 52, grouped as assigned at randomization, with p-value and hazard ratio (HR) for the difference.

The same analysis methods described in Section 5.4.1.1 will be used in this supplementary analysis.

